10.1 Definition of adverse events and reporting requirements

10.1.1 Adverse events

An adverse event (AE) is any untoward medical occurrence (e.g. any unfavorable and unintended sign [including abnormal laboratory findings], symptom or disease) in a clinical investigation participant after providing written informed consent for participation in the study. Therefore, an AE may or may not be temporally or causally associated with the use of a medicinal (investigational) product.

The investigator has the responsibility for managing the safety of individual participant and identifying adverse events.

Novartis qualified medical personnel will be readily available to advise on trial related medical questions or problems.

The occurrence of adverse events must be sought by non-directive questioning of the participant at each visit during the study. Adverse events also may be detected when they are volunteered by the participant during or between visits or through physical examination findings, laboratory test findings, or other assessments.

Adverse events must be recorded under the signs, symptoms, or diagnosis associated with them, accompanied by the following information (as far as possible) (if the event is serious refer to Section 10.1.2):

1. The Common Toxicity Criteria (CTC) AE grade (1-4)

If CTCAE grading does not exist for an adverse event, use:

- 1 = mild: usually transient in nature and generally not interfering with normal activities
- 2 = moderate: sufficiently discomforting to interfere with normal activities
- 3 = severe: prevents normal activities

- 4 =life threatening
- 2. Its relationship to the study treatment. If the event is due to lack of efficacy or progression of underlying illness (i.e. progression of the study indication) the assessment of causality will usually be 'Not suspected.' The rationale for this guidance is that the symptoms of a lack of efficacy or progression of underlying illness are not caused by the trial drug, they happen in spite of its administration and/or both lack of efficacy and progression of underlying disease can only be evaluated meaningfully by an analysis of cohorts, not on a single participant
- 3. Its duration (start and end dates) or if the event is ongoing, an outcome of not recovered/not resolved must be reported
- 4. Whether it constitutes a SAE (see Section 10.1.2 for definition of SAE) and which seriousness criteria have been met
- 5. Action taken regarding with study treatment.

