12.5.2 Safety endpoints

For all safety analyses, the safety set will be used. All listings and tables will be presented by treatment arm.

In particular, summary tables for adverse events (AEs) will summarize only on-treatment events, which started or worsened during the on-treatment period (treatment-emergent AEs).

Adverse events

All information obtained on adverse events will be displayed by treatment group and participant.

The number (and percentage) of participants with treatment emergent adverse events (events started after the first dose of study medication or events present prior to start of double-blind treatment but increased in severity based on preferred term) will be summarized in the following ways:

- by treatment, primary system organ class and preferred term.
- by treatment, primary system organ class, preferred term and maximum severity.
- by treatment, Standardized MedDRA Query (SMQ) and preferred term.

Separate summaries will be provided for study medication related adverse events, death, serious adverse events, other significant adverse events leading to discontinuation, and adverse events leading to dose adjustment.

In addition, a separate listing of death including on treatment and post treatment deaths will be provided.

Clinical laboratory evaluations

All laboratory data will be listed by treatment arm, participant, and visit/time and if normal ranges are available abnormalities will be flagged. Summary statistics will be provided by treatment arm and overall. Shift tables using the low/normal/high/ (low and high) classification will be used to compare baseline to the worst on-treatment value.

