2.8 Safety analyses

2.8.1 Adverse events (AEs)

An adverse event (AE) is any untoward medical occurrence (i.e., any unfavorable and unintended sign [including abnormal laboratory findings], symptom or disease) in a participant or clinical investigation of a participant after providing written informed consent for participation in the study. That means that a participant can report AEs before having started study medication. For reporting purposes, the main focus will be on any adverse event which started on or after the Week 0 visit.

The number (and percentage) of participants with AEs will be summarized by cohort in the following ways:

- by primary SOC and PT
- by primary SOC, PT and maximum severity
- by Standardized MedDRA Query (SMQ) and PT

Separate summaries will be provided for:

- serious adverse events (SAEs)
- AEs leading study discontinuation

Separate summaries will be presented for data collected during the Extension Period.

The MedDRA version used for reporting the study will be described in a footnote. If a particular Missing CTCAE grade will not be imputed. If a participant reported more than one AE with the same PT, the AE with the greatest severity will be presented. A participant with multiple AEs within a primary SOC is only counted once towards the total of the primary SOC.

All AEs will be listed by cohort.

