2.14 Interim analysis

For the purpose of earlier dissemination of results, an interim analysis will be performed after:

- all enrolled participants have completed the Investigational Period or discontinued the Investigational Period prematurely OR
- On/around March 29, 2021, whichever comes first.

Since there will be no hypothesis testing involved, statistical adjustment for the interim analysis will not be made at the stage of final analyses.

3 Sample size calculation

Sample size calculations were based on the proportion of participants who responded to influenza vaccination.

The sample size of 20 participants per arm is selected based on budget and need for early availability of results. The sample size of 20 subjects will provide estimates with margin of error (half-width of a 95% confidence interval) of 20.1%, 19%, and 17.5% corresponding to response rates of 70%, 75%, and 80%, respectively. Adjusting for 10% drop-out, 22 subjects will be enrolled in each arm.

4 Change to protocol specified analyses

There are no changes to protocol specified analyses.

5 Appendix

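### The SAP omits two AE summaries that the protocol specifies (related AEs and AEs leading to dose adjustment) and does not record the omission as a change

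*SAP*

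**What the plan says.** Protocol section 12.5.2 sets out the AE reporting: "Separate summaries will be provided for study medication related adverse events, death, serious adverse events, other significant adverse events leading to discontinuation", and, as the last item of the same sentence, "adverse events leading to dose adjustment". Protocol section 10.1.1 requires each AE to be recorded with, among other things, "Its relationship to the study treatment".

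SAP section 2.8.1 tabulates AEs by system organ class and preferred term, by these with maximum severity, and by Standardized MedDRA Query. It then gives a short list under "Separate summaries will be provided for" with two entries: SAEs and "AEs leading study discontinuation". SAP section 2.8.2 lists all deaths and tabulates them only if there are five or more. SAP section 4 states: "There are no changes to protocol specified analyses". The SAP introduction names protocol version 00 (10 November 2020) as the version it implements. The protocol supplied is amended version 03.

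**The concern.** Safety is among the stated objectives in both documents. Investigators judge causality for every AE, and the protocol says the result will be summarized. A programmer working from the SAP alone would produce no such table, and a reader of SAP section 4 would have no sign that anything had been left out.

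A second matter decides whether a restored table could be read. Participants in Cohorts 1 and 2 receive both the influenza vaccine and ofatumumab, and those in Cohort 3 receive the vaccine and an iDMT. The two documents do not use the same terms for these products. Unless the table says which of them a related AE is related to, its counts could be taken to describe the vaccine, ofatumumab or the combination.

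**Working it through.** No figure in the plan needs to be reproduced. The check is a comparison of the two lists and of the treatment terms.

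**Step 1: the separate AE summaries, item by item.**

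| Summary in Protocol 12.5.2 | Where the SAP provides it |
|---|---|
| Study-medication-related AEs | Nowhere |
| Deaths | 2.8.2 (listed; tabulated from five cases upward) |
| SAEs | 2.8.1 |
| AEs leading to discontinuation | 2.8.1 (worded as study discontinuation) |
| AEs leading to dose adjustment | Nowhere |

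Protocol items: 5. Items with a counterpart in the SAP: 3. Absent: 5 − 3 = 2. The general AE tables in SAP 2.8.1 do not fill the gap, because none is split by relationship. Elsewhere in the SAP, relationship appears only in the date-imputation rules of the appendix, where it means the timing of a partial date.

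**Step 2: could the omission have been correct for the protocol version the SAP cites?** Version 00 is not supplied. The amendment rationales describe an added Guillain-Barré exclusion and site vaccine supply (Amendment 1); the Cohort 2 extension option, dosing relative to the titer sample and an inclusion wording (Amendment 2); and an extra season with a second interim analysis (Amendment 3). None mentions AE summaries. Version 00 therefore probably had the same list, but this is an inference.

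**Step 3: what does study treatment refer to?**

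- The protocol glossary covers any drug or combination given under the study procedures, including background therapy.
- Protocol 6.1.1 puts both ofatumumab and the quadrivalent vaccine under the study treatments.
- SAP 2.1.1 makes the vaccine the investigational treatment and classes ofatumumab and iDMT as additional treatment.

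A related-AE table made under the SAP's terms could thus mean something different from one made under the protocol's. All three cohorts receive two products: up to 44 participants in Cohorts 1 and 2 (vaccine plus ofatumumab) and 22 in Cohort 3 (vaccine plus iDMT), 44 + 22 = 66 in all.

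**Step 4: how far can dates separate the products?** AE start dates are recorded, vaccination is documented, and at-home dose dates go into a diary. In Cohort 1 the vaccine is given before Week 0 and ofatumumab starts at Week 2, so an AE that begins before the first ofatumumab dose cannot be due to it. After that dose in Cohort 1, and throughout Cohort 2, onset alone does not separate the two.

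**The case against.** The strongest reply has four parts.

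*The SAP's statement of no changes is about version 00.* This stands as a limit. A reader might infer that the statement was false when written; that cannot be shown without version 00. What can be shown is that the SAP does not implement the current protocol.

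*The information is not lost.* This is also true. SAP 2.8.1 lists all AEs by cohort and SAP 2.1 lists all data. But a listing gives no counts or percentages by cohort, and the protocol promised summaries.

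*The dose-adjustment table has little to show.* Largely accepted. Protocol 6.5 does not permit dose escalation or modification. Protocol 10.1.1 nevertheless includes dose reduction, increase and interruption among the actions recorded for an AE, so those passages should be reconciled when deciding whether to keep the table. Interruption is not in the 12.5.2 list, and adding it would extend the protocol rather than restore it.

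*Causality by product was never promised.* Correct. A reader might go further and infer that causality is captured only once per AE, so that a suspected event in Cohorts 1 and 2 cannot be assigned to either product. The documents do not support this. Protocol 10.1.1 says what must accompany an AE, not how the eCRF is laid out, and a separate entry per product is compatible with its wording. Dates also allow part of the attribution, as Step 4 shows. Requiring a new causality split would need a protocol amendment and a retrospective judgement of AEs from earlier seasons, which is hard to justify in a descriptive study of up to 66 participants.

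**Conclusion.** The point holds as a mismatch between protocol and SAP. Two of the five separate AE summaries in Protocol 12.5.2 have no counterpart in the SAP, and SAP section 4 does not say so. The related-AE summary is the material one; the dose-adjustment summary may carry little information. The finding rests on the current protocol. Its extension to version 00 assumes that the amendments left the AE summaries alone, as their rationales suggest.

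The differing terms for study treatment are a reason to label the restored table clearly. They do not demonstrate a fault in data capture, because the eCRF is not available. The effect is confined to safety reporting; the primary and secondary antibody analyses do not depend on it.

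**What to change.** 1. Add to SAP 2.8.1 a by-cohort summary of AEs suspected to be related to study treatment.
2. Either add the summary of AEs leading to dose adjustment, or record and justify its removal in SAP section 4.
3. State in the related-AE table which products study treatment covers.
4. Check the eCRF. If it records causality per product, tabulate by product. If it does not, add a footnote that attribution is to the combined regimen, and show AE onset relative to the vaccination date and the first ofatumumab dose, where those dates are available. The vaccination date should be used as such, because SAP 2.1.1 counts study days from the Week 0 visit and the protocol places vaccination before that visit.
5. Update the protocol version cited in the SAP introduction, so that section 4 is a statement about the protocol in force.

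The cost is one or two extra tables and a short SAP revision. No new data field, protocol amendment or re-judgement of past AEs is needed.

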1.2 Purpose

Vaccinations against influenza comprise an important strategy for effective management of participants with MS. Ofatumumab is a human anti-CD20 monoclonal antibody (mAb) that induces B-cell depletion. Considering the role of B-cells in immune-mediated responses, participants treated with ofatumumab may be at an increased risk of developing influenza. They also may incur an increased chance of morbidity and mortality should they become infected. Therefore, it is important to assess if participants treated with ofatumumab are able to mount protective immune responses against the influenza vaccine.

2 Objectives and endpoints

Table 2-1 Objectives and related endpoints

Objective(s) Endpoint(s) **Primary Objective(s)** Endpoint(s) for primary objective(s) Achieving seroprotection as defined by To characterize those achieving seroprotection after receiving the 2020a postvaccination antibody titer ≥ 40 2021, 2021-2022, or 2022-2023 seasonal (ves/no) quadrivalent influenza vaccine in participants treated with ofatumumab 20 mg sc once every 4 weeks Secondary Objective(s) Endpoint(s) for secondary objective(s) To characterize those achieving Achieving seroconversion as defined by seroconversion after receiving the 2020either: (a) a ≥4-fold increase in 2021, 2021-2022, or 2022-2023 seasonal Hemagglutination Inhibition (HI) titers quadrivalent influenza vaccine in after vaccination (in participants with participants treated with ofatumumab 20 mg prevaccination HI titers ≥10) or (b) sc once every 4 weeks postvaccination HI titers ≥40 (in participants with prevaccination HI titers Safety <10) (yes/no) Change in HI titers AEs, SAEs, events leading to discontinuation

2.1 **Primary estimands**

The primary clinical question of interest is: Do relapsing MS participants who receive ofatumumab treatment mount an immune response to the 2020-2021, 2021-2022, or 2022-2023 influenza vaccine?

The justification for the primary estimand is that it will capture whether of atumum ab treated participants generate antibodies to influenza vaccine as assessed by HI titers.

The primary estimand is described by the following attributes:

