Participants who discontinue study treatment or who decide they do not wish to participate in the study further should NOT be considered withdrawn from the study UNLESS they withdraw their consent (see Section 9.1.2 'Withdrawal of Informed Consent' section). Where possible, they should return for the EOS Visit applicable to the period in which the patient is currently in. Participants in Cohort 1 that discontinue in the Investigational Period, should return for all assessments indicated for the EOS1 Visit except for study drug administration. Participants in Cohort 1 and 2 that discontinue in the Extension Period, should return for all assessments indicated for the EOS2 Visit except for study drug administration. At EOS visits all dispensed study drug to participants in Cohort 1 and Cohort 2 should be reconciled and the adverse event and concomitant medications should be recorded on the CRF (for participants in both arms). If they fail to return for these assessments for unknown reasons, every effort (e.g. telephone, e-mail, letter) should be made to contact the participant/pre-designated contact as specified in the lost to follow-up section. This contact should preferably be done according to the study visit schedule.

If the participant cannot or is unwilling to attend any visit(s), the site staff should maintain regular telephone contact with the participant, or with a person pre-designated by the participant. This telephone contact should preferably be done according to the study visit schedule.

After study treatment discontinuation, at a minimum, in abbreviated visits, the following data should be collected at clinic visits or via telephone/email contact:

- New / concomitant treatments
- Adverse Events / Serious Adverse Events

The investigator must also contact the IRT to register the participant's discontinuation from study treatment.

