1.2 Study objectives and endpoints

Study objectives and associated endpoints are shown in Table 1-1.

Table 1-1 Study objectives and endpoints

Objective(s) Endpoint(s) Primary objectives(s) Endpoint(s) for primary objective(s) To characterize those achieving Achieving seroprotection as defined by a seroprotection after receiving the 2020post-vaccination antibody titer ≥40 at 2021 seasonal quadrivalent influenza Week 4 (yes/no) vaccine in participants treated with ofatumumab 20 mg sc once every 4 weeks Secondary objective(s) Endpoint(s) for secondary objective(s) To characterize those achieving Achieving seroconversion at Week 4 as seroconversion after receiving the 2020defined by either: 2021 seasonal quadrivalent influenza a. a ≥4-fold increase in HI titers vaccine in participants treated with after vaccination (in participants ofatumumab 20 mg sc once every 4 with pre-vaccination HI titers weeks ≥10) or Safety

Objective(s)	Endpoint(s)
	b. post-vaccination HI titers ≥40 (in participants with pre-vaccination HI titers <10) (yes/no)
	 Change in HI titers
	 AEs, SAEs, AEs leading to discontinuation

2 Statistical methods

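### The SAP counts only AEs leading to study discontinuation, so an AE that stops ofatumumab in a participant who stays in the study is not counted under the discontinuation endpoint

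*SAP*

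**What the plan says.** **Endpoint.** Protocol Table 2-1 lists "AEs, SAEs, events leading to discontinuation" and SAP Table 1-1 lists "AEs, SAEs, AEs leading to discontinuation". Neither says what is discontinued.

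**Planned summaries.** Protocol 12.5.2 plans separate summaries of study-medication-related AEs, deaths and SAEs, and of "other significant adverse events leading to discontinuation, and adverse events leading to dose adjustment". SAP 2.8.1 plans separate summaries for two items only: SAEs and "AEs leading study discontinuation". SAP 2.8.2 lists all deaths but tabulates them only if there are 5 or more.

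**Stopping treatment versus leaving the study.** The protocol glossary defines study treatment discontinuation as permanently stopping study drug, and says it may or may not coincide with study discontinuation. Protocol 9.1.1 says: "Participants who discontinue study treatment or who decide they do not wish to participate in the study further should NOT be considered withdrawn". The one exception it makes is withdrawal of consent. It also requires AEs and new treatments to be collected after treatment stops.

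**Declared changes.** SAP section 4 states: "There are no changes to protocol specified analyses".

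**The concern.** Protocol 9.1.1 foresees AEs that end study treatment. Its mandatory reasons for stopping include PML, active serious infection, severe skin reactions, hypersensitivity and malignancy. These are the events a reader of the discontinuation endpoint would most want to see, since they describe whether patients can stay on ofatumumab.

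If the participant stops the drug but stays in follow-up, as 9.1.1 allows, the AE does not meet the SAP's criterion. The clinical study report could then show no AEs leading to discontinuation although ofatumumab had been stopped because of an AE. The table would be correctly labelled, but the endpoint in Table 1-1 would be only partly reported.

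**Working it through.** No power, alpha or rate enters this point, and the plan states no figure to reproduce. The check sets the texts side by side.

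**Step 1. Which AE-driven stops reach the SAP's discontinuation table?**

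| What happens after the AE | Leads to study discontinuation? | In the SAP 2.8.1 discontinuation table? |
|---|---|---|
| Drug stopped for good; participant stays in the study and is followed under Protocol 9.1.1 | No | No |
| Drug stopped; participant leaves the study early through an EOS visit (Protocol section 8; SAP 1.1), consent not withdrawn | Can be recorded so | Yes, if so recorded |
| Drug stopped; participant withdraws consent because of the AE | Yes | Yes |

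The gap is the first row.

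**Step 2. Does another SAP output identify the first-row events as discontinuations?** SAP 2.3.1 lists participants who discontinued from the study, with the primary reason. That is the same restriction, so it does not recover them. SAP 2.4.1 summarizes the number of injections taken but does not link it to AEs. The overall AE tables, the AE listing and the SAE table show the event, but none of them counts it as leading to discontinuation.

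**Step 3. Compare the five separate summaries in Protocol 12.5.2 with the SAP.**

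| Protocol 12.5.2 | SAP 2.8.1 and 2.8.2 |
|---|---|
| SAEs | Kept |
| AEs leading to discontinuation | Narrowed to study discontinuation |
| Study-medication-related AEs | Absent |
| AEs leading to dose adjustment | Absent |
| Deaths | Listed always; tabulated only at 5 or more |

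One is kept, one narrowed, two absent and one made conditional (1 + 1 + 2 + 1 = 5). SAP section 4 records none of this.

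**Step 4. Are the data there?** Protocol 10.1.1, item 5 under the AE record, collects "Action taken regarding with study treatment", and the options printed after it include drug interruption and withdrawal, shown as a single combined item. Protocol 9.1.1 asks the investigator to record the primary reason for premature treatment discontinuation and to register it in the IRT. So either the action taken or the recorded reason should identify the event.

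**Step 5. Granularity.** With planned enrolment of 22 per cohort, one event is 1/22 = 4.5 percentage points of a cohort, or 1/44 = 2.3 points across Cohorts 1 and 2. These figures say what one event weighs in the table. They do not measure bias, because the documents give no rate of AE-driven treatment stops.

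**The case against.** **The endpoint does not say what is discontinued, and the SAP chose one reading.** This stands in part: no explicit definition is contradicted. SAP 2.1.1 calls the single-dose vaccine the investigational treatment and ofatumumab additional treatment, and study discontinuation is a criterion that applies to all three cohorts. But Protocol 6.1.1 lists ofatumumab among the study treatments, and a one-off vaccine cannot be discontinued once given. The SAP has narrowed an open term without saying so.

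**Participants who stop treatment may be counted anyway.** This also stands in part. A reader might infer from Protocol 9.1.1 that every AE-driven stop without consent withdrawal is missed by definition. The documents do not support that. The sentence about "Participants who discontinue study treatment or who decide they do not wish to participate in the study further" limits only the label of withdrawn. Protocol section 8 and SAP 1.1 describe premature study discontinuation with its own EOS visit and attach no consent condition. Stopping ofatumumab early in Cohort 1 and then attending EOS1 fits either description, because both routes lead to that visit. The count may therefore depend on how a site records the case, which is a reason to define the endpoint.

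**The events are reported elsewhere.** True. All AEs are listed, SAEs have their own table, and Protocol 10.1.2 makes every new malignancy serious unless it is progression of the study indication. What is missing is the count under the stated endpoint.

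**The other omissions matter little.** Largely true. Protocol 6.5 does not permit dose modification, so a dose-adjustment table would hold little. Deaths are all listed and, being SAEs, are in the SAE table. The related-AE summary is the one plain omission.

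**SAP section 4 refers to a protocol version that is not available.** The SAP cites version 00, and the comparison here is with amended version 03. The amendment summaries mention no change to AE tables, so the text is probably the same, but this cannot be confirmed.

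**Conclusion.** The point holds within limits. SAP 2.8.1 under-counts a stated secondary safety endpoint for one group: participants whose ofatumumab is permanently stopped for an AE and who remain in the study. A reader might go further and infer that such events vanish from the report, or that several safety summaries are lost. Neither follows, for the reasons given above.

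The size cannot be put as an expected number of events. The conclusion assumes that study discontinuation in SAP 2.8.1 carries its ordinary meaning, distinct from stopping treatment as in the protocol glossary. The statement that SAP section 4 is inaccurate assumes that section 12.5.2 was the same in protocol version 00.

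The primary seroprotection analysis is untouched and no hypothesis test is involved. The correction is still worth making, because it is cheap and the endpoint is named in both documents.

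**What to change.** 1. In SAP 2.8.1, add a summary by cohort and period of AEs leading to permanent discontinuation of the named drug: ofatumumab in Cohorts 1 and 2, and iDMT in Cohort 3 if that is collected. The drug must be named, because study treatment alone could be read as the vaccine.
2. Derive it from the action taken recorded with each AE. If the CRF does not separate interrupted from withdrawn, use the recorded primary reason for treatment discontinuation. Check that the field also covers commercially prescribed ofatumumab in Cohort 2.
3. Keep AEs leading to study discontinuation as a separate row.
4. Restore the summary of study-medication-related AEs.
5. Record any remaining departure from Protocol 12.5.2 in SAP section 4, namely the dose-adjustment table and the five-death threshold, with a short reason for each.

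The cost is SAP wording and one or two small tables. No new data collection should be needed, provided the CRF holds the fields that Protocol 9.1.1 and 10.1.1 describe; the CRF itself was not available to check.

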Participants in Cohort 2 will continue to administer of atumumab monthly until the final dose at Week 28. Novartis will supply of atumumab to participants in Cohort 2 for the Extension Period.

Cohort 2 participants may either remain on their commercially prescribed of atumumab or switch to study supplied of atumumab.

Participants in Cohort 3 will not enter the open-label Extension Period.

Study design schematics for Cohorts 1, 2 and 3 are shown in Figure 3-1, Figure 3-2 and Figure 3-3 respectively.

Figure 3-1 Study Design (Cohort 1)

[figure not shown]
[figure not shown]

Figure 3-2 Study Design (Cohort 2)

[figure not shown]

Figure 3-3 Study Design (Cohort 3)

4 Rationale

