2.1 Data analysis general information

The statistical analysis outlined in this SAP will be performed by Novartis or a designated Contract Research Organization (CRO), using SAS® version 9.4 or higher and stored in the Novartis Global Programming and Statistical Environment (GPS).

For continuous variables, summary statistics will include number of participants (n), mean, standard deviation, minimum, maximum, median and 25th and 75th percentiles (optional). For categorical variables, frequency counts and percentages will be reported.

Unless otherwise stated, all data summaries will be presented by cohort and on all participants in the respective analysis set.

The CSR analysis cut-off date will be the EOS1/EOS visit for participants who do not continue to the Extension Period, or the EOS2 visit for participants who continue into the Extension Period. All data collected prior to this date will be used for analysis.

All data (collected or derived) will be listed appropriately.

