2.2 Analysis sets

Safety set

The Safety Set (SAF) comprises all participants who have received the 2020-2021 inactivated influenza vaccine.

Unless stated otherwise, the SAF will be used for all summary tables and listings.

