2.3 Patient disposition, demographics and other baseline characteristics

2.3.1 Patient disposition

Patient disposition will be summarized for the following study periods: screening, treatment, extension treatment and treatment assigned.

Patient disposition for each period will be summarized for all participants who entered that period. Participants who have entered any study period but have discontinued from the study will be listed as appropriate along with the primary reason for discontinuation.

The number and percentage of screening failures and the reason for screening failure will be presented for all screened participants.

For each protocol deviation, the number and percentage of participants for whom the deviation applies will be tabulated.

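### Extension-period AE percentages default to the whole Safety Set of each cohort, so Cohort 1 and 2 participants who never entered the optional extension stay in the denominator

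*SAP*

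**What the plan says.** SAP 2.8.1 sets out the AE tables: "The number (and percentage) of participants with AEs will be summarized by cohort in the following ways". It puts the main focus on events starting on or after the Week 0 visit. It then adds that "Separate summaries will be presented for data collected during the Extension Period", without naming a population or denominator.

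The population therefore comes from the general rules. SAP 2.2: "Unless stated otherwise, the SAF will be used for all summary tables and listings". SAP 2.1: "Unless otherwise stated, all data summaries will be presented by cohort and on all participants in the respective analysis set". The set itself is defined by vaccination: "The Safety Set (SAF) comprises all participants who have received the 2020-2021 inactivated influenza vaccine". Protocol 12.5.2 also applies the safety set to every safety analysis; Protocol 12.1 defines that set by receipt of at least one dose of study drug. Neither definition depends on entering the extension, and neither document defines an extension set.

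Entry is optional for Cohorts 1 and 2 (Protocol section 3; SAP 1.1). For the reference cohort, Protocol section 3 states: "Participants in Cohort 3 will not enter the open-label Extension Period".

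SAP 2.3.1 does use a period-specific population, but only for disposition: "Patient disposition for each period will be summarized for all participants who entered that period".

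**The concern.** A participant who leaves at or before EOS1 cannot have an event in the Extension Period. Counting that person in the denominator dilutes the percentage for those who were at risk. Safety is a listed objective, and Cohort 2 can receive study-supplied ofatumumab only in the extension, so these tables carry much of the on-study safety information.

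Because the disposition rule has no counterpart in 2.8.1, two programmers could produce different tables from the same plan. One who applies the stated default uses the cohort's SAF count. One who assumes that the disposition rule carries over uses entrants.

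A related gap concerns the main three-cohort AE table. SAP 2.8.1 gives it a start at Week 0 but no end. SAP 2.1 uses all data up to EOS1/EOS or, for those who continue, EOS2. Extension events are to be summarized separately, but the text does not say that they are left out of the main table. Cohort 3 is followed only to Week 4, while Cohorts 1 and 2 can run to Weeks 26 and 28.

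**Working it through.** **Inputs.** Planned cohort size is 22 (SAP section 3; Protocol 12.8.1), the largest per-cohort SAF at the planned size. The plan reaches it as 20 × 1.10 = 22. The documents state no extension uptake and no extension AE rate, so the number of entrants and the 3 events below are assumptions.

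**Denominator effect.** Let *r* be entrants with an event, *e* the entrants, and *n* the cohort SAF.

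- Percentage under the SAF default: *r*/*n*.
- Percentage among those at risk: *r*/*e*.
- Hence *r*/*n* = (*r*/*e*) × (*e*/*n*): the reported figure is the entrant figure times uptake.

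With *r* = 3 and *n* = 22:

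| Entrants | Uptake | SAF default | Among entrants |
|---|---|---|---|
| 11 | 0.50 | 3/22 = 13.6% | 3/11 = 27.3% |
| 15 | 0.68 | 3/22 = 13.6% | 3/15 = 20.0% |
| 18 | 0.82 | 3/22 = 13.6% | 3/18 = 16.7% |
| 20 | 0.91 | 3/22 = 13.6% | 3/20 = 15.0% |
| 22 | 1.00 | 3/22 = 13.6% | 3/22 = 13.6% |

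The effect is a halving at 50% uptake and nothing at full uptake.

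**Cohort 3.** The tables are by cohort, so *n* for Cohort 1 or 2 never includes Cohort 3, and removing Cohort 3 changes neither percentage. It would matter only in a pooled column: 6 events would give 6/66 = 9.1% against 6/44 = 13.6%. SAP 2.8.1 plans no such column.

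**Main AE table, if extension events were included.** Assume the same 10% risk per 4 weeks in every cohort, and that every entrant completes the extension.

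- Cohort 3, 4 weeks: 10%.
- Followed to Week 26: 1 − 0.90^(26/4) = 49.6%.
- Followed to Week 28: 1 − 0.90^(28/4) = 52.2%.

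The last two figures require full uptake. With 12 of 22 entering, Cohort 1 would show (12 × 49.6% + 10 × 10%)/22 = 31.6%. With 8 of 22 it would show (8 × 49.6% + 14 × 10%)/22 = 24.4%. Follow-up alone could therefore separate the cohorts, by an amount that also depends on uptake.

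**The case against.** The SAP never states that extension percentages use the whole SAF; that follows from a default. Elsewhere it does work by period: disposition counts those who entered, and SAP 2.4.1 summarizes injections by cohort and period. An analyst might well use entrants anyway. No hypothesis is tested, all AEs are listed by cohort, and disposition will report how many entered, so a reader could recompute the percentages.

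This limits the consequence but does not remove the problem. The default is explicit, 2.8.1 does not override it, and the disposition rule does not extend to AEs. Applied as written, the plan prints a percentage with the wrong denominator, and readers should not have to correct it.

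A reader might infer more than the documents support:

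- **That Cohort 3 dilutes the ofatumumab results.** It does not, because the tables are by cohort. The documents do not specify a Cohort 3 column in the extension tables, so a misleading 0% there is conjecture.
- **That the main AE table certainly mixes periods.** The natural reading of separate extension summaries is that extension events are reported apart. Mixing is a possible reading that the text fails to exclude.
- **That almost all study-supplied ofatumumab exposure falls in the extension.** By dose count this is wrong. In Protocol Table 8-1 a Cohort 1 completer takes three doses in the Investigational Period and six in the extension, so one third come before it. Cohort 2 participants may also stay on commercial supply during the extension.

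**Conclusion.** The point holds for Cohorts 1 and 2. Under the plan's own defaults, non-entrants are counted in extension AE percentages, which are thereby multiplied by the uptake fraction. This is more than missing detail, because the stated default leads to the wrong denominator.

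Whether the risks will in fact be understated, and by how much, depends on an uptake that the documents do not give. The documents support saying that they can be understated, not that they are. The illustrated range rests on 3 events in a cohort of 22. The protocol and SAP define the safety set differently, but this does not affect the conclusion, because neither definition requires extension entry.

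The end point of the three-cohort AE table is a secondary clarification.

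**What to change.** 1. In SAP 2.2, define an Extension Set: SAF participants in Cohorts 1 and 2 who entered the Extension Period, in line with the disposition rule in SAP 2.3.1. Use it as the by-cohort denominator for all extension safety tables and omit Cohort 3 from them.
2. In SAP 2.8.1, state that the three-cohort AE table covers events from the existing Week 0 start through EOS1/EOS.

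The cost is a few lines of SAP text and one population flag. The Extension Set is a subset of the SAF. SAP section 4, which now reports no changes to protocol-specified analyses, can record the narrower denominator. The small downside is that extension percentages rest on fewer participants and, when uptake is incomplete, will be higher than under the default.
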